5.2.3 Exploratory Endpoints

- ST2 EIA (Presage, Critical Diagnostics)
- Reg3a EIA
- Ceruloplasmin EIA
- elafin EIA
- endotoxin activity assay (EAA, Spectral Diagnostics)
- Gut and urine microbiome sequencing of 16S rRNA DNA, to generate Shannon Diversity index and ration of Clostridia : Lactobacilli, and *firmicutes* vs. *bacteroidetes* vs. *Enterococci* species
- PBMC ROCK activity as measured by ratio of Phosphorylated : Total MBS in cryopreserved PBMCs, ROCK enzyme protein levels by WB
- Percentages of CD4+ and CD8+ cells expressing FoxP3 and CD73 or CD39, percentages of CD4+ CD146+CCR5+ cells, and percentages of a4b7 cells expressing CD39 or CD73.

5.3 Treatment Schedule

5.3.1 Standard GvHD Prophylaxis

All subjects will receive a standard GvHD prophylaxis regimen selected at the discretion of their transplant physician. The standard GvHD prophylaxis utilized at the study site includes:

- Tacrolimus 0.03 mg/kg/day by continuous infusion starting on day -2 pre-transplantation, adjusted as needed to achieve a serum level of 10-15 mcg/mL, and
- Methotrexate 5 mg/m² given IV on days +1, 3, 6, and 11 after transplantation.

While a tacrolimus/methotrexate-based regimen is used after a variety of transplant conditioning regimens and for a variety of diseases, alternate standard regimens may be used. The standard GvHD prophylaxis regimen is not dictated by this protocol. GvHD prophylaxis regimens utilizing an investigational agent (other than telmisartan) are prohibited.

5.3.2 Telmisartan Dosing and Discontinuation of Other Anti-Hypertensive Drugs.

The first five subjects enrolled will discontinue any anti-hypertensive medications they are taking at least 24 hours prior to beginning the telmisartan dose escalation on day -5. For subsequent enrollees, subjects will be asked to discontinue any antihypertensive medications they may be taking at least 48 hours prior to first dose of study medication.

For the purposes of this study, a commercial supply of Micardis brand (Boehringer Ingelheim) of telmisartan tablets will be used due to the superior release kinetics of Micardis compared to several generic brands [105], and to ensure uniformity of product during the trial. All subjects (other than the first 5 enrollees, discussed above) will receive 160 mg telmisartan p.o. once daily starting two days prior to HCT (Day -2) and continuing for 101 days (until Day +98 post-HCT), unless discontinued early from treatment. Subjects will be instructed to take their study medication at approximately the same time every day, before bedtime, or upon waking, but there are no strict requirements for the timing of administration. Downward dosing adjustments will be made according to the steps outlined in section 5.3.4.

5.3.3 Treatment Compliance

Most patients will be discharged within 2- 3 weeks following HCT. Upon discharge patients will be given drug diaries to complete as they take their daily study medication at home. Subjects will be instructed to bring their study medication and drug diaries to all follow-up appointments at the John Theurer Cancer Center at HackensackUMC. Compliance will be monitored by the study team during the treatment period. Missed days of medication will be noted. Five missed doses over any 2 week period for reasons other than hypotension or other side effects, will be considered non-compliance. Patients who are non-compliant *prior to* 14days post-HCT will be withdrawn from the study. Subjects who are non-compliant *after* 14 days post-HCT will be allowed to continue on study treatment with counseling on compliance.

5.3.4 Dose Modifications

Blood pressure will be monitored every 4 hours, as per standard operating practice for HCT patients, during the initial hospital stay, including pre- and post-transplant periods. If hypotension does occur during the initial treatment phase in the hospital, the patient will be placed in the supine or reverse Trendelenburg position and, if necessary, given an intravenous Telmisartan for GVHD in HCT

infusion of normal saline. A transient hypotensive response is not a contraindication to further treatment, which usually can be continued without difficulty once the blood pressure has stabilized.

Prior to discharge, patients are taught how to use an automated blood pressure cuff, and are given such a cuff upon discharge from the hospital with instructions to take their blood pressure at home twice a day. Patients are instructed to keep a diary of their systolic and diastolic blood pressure readings and to bring the diary with them to their clinic visits. They are also instructed to contact their transplant clinical caretaker for any symptoms of low blood pressure, as per SOP of the Blood and Marrow Transplantation Program of Hackensack University Medical Center.

Subjects who develop grade 3 or 4 hypotension as defined by CTCAEv4, while receiving telmisartan as their only anti-hypertensive medication will skip one daily dose of telmisartan and resume dosing the following day at 80 mg/day. Subjects who experience grade 3 or 4 hypotension on 80 mg/day will again skip one daily dose of telmisartan and resume dosing the following day at 40 mg/day. Subjects who experience grade 3 or 4 hypotension on 40 mg/day, and cannot tolerate re-initiation of 40 mg/day after a one day drug hiatus, will be discontinued from study treatment.

Subjects who develop grade 3 or 4 hypotension while on telmisartan plus one or more additional anti-hypertensive drugs will follow the same algorithm for telmisartan dose reduction described above, and the non-telmisartan anti-hypertensive drug(s) will not be re-started with the next doses of telmisartan unless additional anti-hypertensive treatment is required even after the 160 mg daily dose of telmisartan has been re-established.

In addition to the above adjustments for hypotension, telmisartan will be dose adjusted by the same guidelines for grade 3 or greater drug related adverse events and will be stopped for angioedema.

Whenever a dose reduction has occurred, patients who tolerate the reduced dose for one week will be increased to the next highest dose. If that dose is also tolerated for one week, the dose will again be increased until the original 160 mg/day dose is achieved. If a re-escalation results in reappearance of hypotension or other drug-related side effects, the medication will be stopped for one day, and the subject will receive the previous tolerated dose (as detailed above) for the remainder of the trial dosing period.

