5.4.2 Agents That Increase the Risk of Renal Failure

Hyperkalemia may occur in patients on telmisartan, particularly in patients with advanced renal impairment, heart failure, on renal replacement therapy, or on potassium supplements, potassium-sparing diuretics, potassium-containing salt substitutes or other drugs that increase potassium levels. Potassium-sparing diuretics such as spironolactone, and angiotensin-

converting-enzyme (ACE) inhibitors will be discontinued prior to start of study and will not be used in conjunction with telmisartan during the study unless deemed necessary by the HCT clinical physicians, due to potential interactions leading to renal toxicity. Potassium supplements will also be discontinued, and re-started gradually if need is indicated by electrolyte monitoring. Foods high in potassium will be limited to safe levels during the period of telmisartan administration except as specifically allowed by the physician monitoring the patient's electrolyte status.

In patients who are elderly, volume-depleted (including those on diuretic therapy), or with compromised renal function, co-administration of NSAIDs, including selective COX-2 inhibitors, with telmisartan, may result in deterioration of renal function, including possible acute renal failure. These effects are usually reversible. Caution will be taken when administering NSAIDs to study subjects, and renal functions will be monitored.

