5.4.3 Impaired Hepatic Function

As the majority of telmisartan is eliminated by biliary excretion, patients with biliary obstructive disorders or hepatic insufficiency can be expected to have reduced clearance. Hepatic function will be closely monitored as part of the standard of care for HCT patients, and increased LFTs or bilirubin will be carefully followed. Careful consideration should be taken before administering any medications that have known hepatic toxicity, especially in patients who experience hepatic insufficiency pre- or post-HCT (e.g., as a result of grade III or IV GVHD).

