5.5 Subject Discontinuation

5.5.1 Discontinuation from Study Treatment

Any subject who prematurely discontinues from study treatment on or after day 14 should still be followed through Day +180 Post HCT for primary, secondary, and exploratory outcomes. Adverse events (AEs) leading to treatment discontinuation of a subject will be followed until resolution, return to baseline, or until the event is considered chronic.

A subject should be withdrawn from the study treatment if, in the opinion of the investigator, it is medically necessary, or if it is the wish of the subject. However every effort should be made to keep the subject on study treatment, especially in cases where the dose or schedule of study treatment can be modified (see section 5.3.3 Dose Modifications). Subjects who discontinue from study treatment on or after day 14 should still complete end of treatment study procedures (clinical evaluations, blood, stool, and urine samples, if they are willing to do so). Subjects may be discontinued from study treatment for any of the following reasons:

- \geq grade 3 hypotension at the 40 mg/day dose level after one attempt at restarting this dose following a 1 day drug hiatus.
- Onset or persistence of any treatment related adverse events (AEs) that, in the opinion of the study physician, warrant discontinuation.
- Non-compliance, defined as five missed doses over any 2 weeks period, for reasons other than hypotension or other side effects, within 14 days post-HCT.
- Significant protocol deviation that would render the subject unevaluable
- Voluntary Withdrawal of consent
- Pregnancy or plan to become pregnant

If a subject wishes to stop study drug or withdraw from the study, their routine standard of care (SOC) medical data to obtain information on the critical safety and efficacy endpoints of the study, including occurrence of aGVHD, engraftment, adverse effects, relapse, and NRM, as well as other recoverable data indicated on Table 3 that is obtained as part of routine SOC will be reviewed on a regular basis up to 180 days post transplant. This will allow us to obtain useful data without requiring any additional telmisartan treatment or sampling.

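### For grade 3 or greater drug-related events other than angioedema, section 5.3.4 restarts telmisartan after one skipped dose and steps it up after a week, with no requirement for recovery or a repeat test

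*Combined protocol and SAP*

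**What the plan says.** Under section 5.3.4 a patient with grade 3 or 4 hypotension on 160 mg "will skip one daily dose of telmisartan and resume dosing the following day at 80 mg/day". A further episode on 80 mg leads, after another one-day skip, to 40 mg. Patients who have an episode on 40 mg and "cannot tolerate re-initiation of 40 mg/day after a one day drug hiatus, will be discontinued from study treatment".

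The section then carries this schedule over to other events: "telmisartan will be dose adjusted by the same guidelines for grade 3 or greater drug related adverse events and will be stopped for angioedema". The upward rule covers every reduction: "Whenever a dose reduction has occurred, patients who tolerate the reduced dose for one week will be increased to the next highest dose". It repeats weekly until 160 mg is reached. If the effect reappears on the way up, drug stops for one day and the patient returns to the previous tolerated dose for the rest of treatment. The only recovery wording in 5.3.4 concerns further treatment after a transient fall in pressure, "which usually can be continued without difficulty once the blood pressure has stabilized".

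Other sections touch on the same events:
- 5.4.2, on potassium: "Potassium supplements will also be discontinued, and re-started gradually if need is indicated by electrolyte monitoring".
- 5.4.3, on the liver: "increased LFTs or bilirubin will be carefully followed".
- 5.5.1, among the reasons to discontinue: "Onset or persistence of any treatment related adverse events (AEs) that, in the opinion of the study physician, warrant discontinuation".
- 6.3 and Table 3 set chemistry panels at Day +7 and at each later study visit: weekly to Day +56, then Days +70, +84, +100 and +180.

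**The concern.** The schedule suits blood pressure. It is measured every four hours in hospital and twice a day at home, so both recovery and tolerance show up without a special order. A potassium, creatinine or bilirubin value is unknown until blood is drawn. Section 1.3.3 names hyperkalaemia, azotaemia and renal failure as risks of this drug, and reduced clearance in hepatic insufficiency. For these events a one-day skip is not evidence of recovery, and a week without symptoms is not evidence of tolerance.

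What is at stake is patient safety on re-challenge. The step-back rule after a failed increase protects a patient only if someone finds the recurrence, and for a laboratory event that takes a test.

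**Working it through.** **1. Is there a recovery or test condition anywhere?** The plan states no figure here, so the first check is of the text.

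| Section | What it provides | Does it govern the telmisartan restart or increase? |
|---|---|---|
| 1.3.3 | Chemistries to confirm normal potassium before telmisartan is started | No: applies to the first start only |
| 5.3.4 | Skip one dose; weekly step-up if tolerated | No grade, baseline or test named; tolerance not defined |
| 5.4.2 | Electrolyte and renal monitoring | No: a result governs potassium supplements, not telmisartan |
| 5.4.3 | Follow-up of LFTs and bilirubin | No |
| 5.5.1 | Physician may discontinue | Withdrawal only; no restart criterion |
| 6.3, Table 3 | Panels at fixed visits | No: not tied to dose changes |
| 9.1, 9.2 | Laboratory AEs limited to those needing intervention or leading to discontinuation; AEs followed to resolution where possible | No |

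**2. How long is the interruption?** One skipped daily dose lengthens the gap between doses from 24 to 48 hours. Section 1.3.5 gives a terminal half-life of about 24 hours, so the skip adds (48 − 24)/24 = 1 half-life.

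**3. An event known to persist at grade 3.** The path is 160 mg, skip, 80 mg, skip, 40 mg, one-day hiatus, one retry at 40 mg, stop. That is at least one dose at 80 mg and two at 40 mg before drug is stopped under 5.3.4.

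**4. An event that is not retested.** Let D be the day the event is found on 160 mg. If the skipped dose falls on D, 80 mg starts on D+1; if on D+1, it starts on D+2. Seven doses at 80 mg follow, so 160 mg is due on D+8 or D+9. The last dose is on Day +98.

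| Found at visit | 160 mg due | Next scheduled panel | Increase precedes panel by | Doses before panel (80 mg + 160 mg) |
|---|---|---|---|---|
| Day +56 | Day 64 or 65 | Day 70 | 6 or 5 days | 13 (7+6) or 12 (7+5) |
| Day +70 | Day 78 or 79 | Day 84 | 6 or 5 days | 13 (7+6) or 12 (7+5) |
| Day +84 | Day 92 or 93 | Day 100 | 8 or 7 days | 14 (7+7) or 13 (7+6) |

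**5. Visit windows of ±3 days.** The shortest gap between the first two pairs of visits is 14 − 6 = 8 days (for example Day 59 to Day 67), against 160 mg due at 8 or 9 days. Of the 7 × 7 = 49 window combinations, the panel comes before the increase in 0 (skip on D) or 1 (skip on D+1). For Day +84 to Day +100 the shortest gap is 16 − 6 = 10 days, so the count is 0 of 49.

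**6. Where the timing point stops.** After a reduction to 40 mg, 160 mg is due on D+15 or D+16. From these visits that is Day 71 or 72, Day 85 or 86, or Day 99 or 100: after the next nominal panel in the first two cases and after dosing ends in the third. Before Day +56 a weekly panel is nominally due before the increase, but 5.3.4 does not make the increase depend on its result.

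**The case against.** The strongest reply is that 5.3.4 does not send a known, persisting grade 3 event back to full dose. The ladder applies at each level, so such an event on 80 mg leads to 40 mg and then off drug. The upward rule requires that the reduced dose be tolerated, and its reference to reappearance suggests that the event had gone. Section 5.5.1 calls for withdrawal when medically necessary and lists persistence of a related event as a ground. All of this stands. A reader might infer that any unresolved event returns to 160 mg. The documents do not support that: it can happen only where no one has retested.

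Testing outside the schedule is also likely. Under 9.1 a laboratory abnormality counts as an adverse event only if it needs intervention or leads to discontinuation, so the patient is already under care. Section 6.3 allows additional standard-of-care assessments. This softens the timing point but does not remove it, because those assessments are optional and no result governs the dose. A reader might also want to express the timing gap as a share of all dosing days. That would count events found between visits, which need an unscheduled test to be found at all, so it cannot also assume that no unscheduled test follows. Only the three visit days are used here.

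The risk should not be overstated either. Section 1.3.3 links azotaemia and renal failure to susceptible patients, whom it regards as unsuitable for transplant. Section 4.1.2 excludes known heart failure and renal impairment needing replacement therapy. Section 1.3.4 reports few drug-related laboratory abnormalities, though in pooled telmisartan studies outside transplantation. The intolerance stopping rule in 8.4 (2 of the first 8) and monthly DSMB review act on the trial; neither sets a condition for the individual patient's next dose.

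**Conclusion.** The point holds. For grade 3 or greater drug-related events other than hypotension and angioedema, the written rule restarts drug after one skipped dose and increases it after a week, and neither step requires recovery or a test. That gap applies throughout dosing, subject to physician withdrawal under 5.5.1.

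The timing point is narrower. It concerns a first reduction from 160 mg at the Day +56, +70 or +84 visit, where 160 mg is due 5 to 8 days before the next scheduled panel on nominal dates. It assumes that 5.3.4 is followed literally, that the week means seven doses, and that no test is done outside the schedule.

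The documents give no rate for these events in transplant patients on telmisartan, so no number of affected patients is offered. Sample size, power and error rates are untouched. The rule should be changed because the safety gain is specific and the change is small.

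**What to change.** Revise 5.3.4 as follows:
- Limit the one-day skip to hypotension. Angioedema still stops drug.
- For any other grade 3 or greater drug-related event, hold telmisartan until recovery (for example grade 1 or less, or baseline), then restart one level lower.
- Allow re-escalation only if a repeat of the relevant test (potassium, creatinine, bilirubin or LFTs) during the week at that level shows no recurrence.
- State whether an event on 40 mg restarts at 40 mg after recovery or stops drug.

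The test windows, and any bar on re-escalation after a grade 4 event, are for the investigator to set.

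The cost is one paragraph in 5.3.4, a footnote to Table 3, some missed doses, and one or two routine chemistry panels per affected patient. Section 5.3.3 already exempts doses missed for side effects from non-compliance. Section 5.5.2 defines evaluable subjects as those who remain on telmisartan through Day +14, so it needs a line saying whether a patient whose hold spans that day is evaluable.

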5.3.5 Occurrence of GvHD

Subjects who experience GvHD during the study treatment period will continue to receive telmisartan through Day +98 post HCT or until treatment discontinuation (see section 5.5). Standard GvHD treatment should be given at the discretion of the subject's transplant physician. While GvHD, especially Grade III-IV GvHD, should be treated accordingly, the specific treatment regimen is not dictated by this protocol. Patients with Grade I GVHD of the skin without any other organ involvement may be treated with a topical corticosteroid cream. Patients with \geq Grade II acute GVHD will be treated with high-dose, systemic corticosteroids. The following

general guidelines promote consistency in our clinical practice but may be modified for individual patients as clinical circumstances warrant:

- a. Grade 0-I GVHD
 - (i) Topical corticosteroids (usually 0.1% triamcinolone; 1% hydrocortisone to face) applied to rash BID.
- b. Grade II-IV GVHD
 - (i) Methylprednisolone or prednisone, 1 mg/kg, BID for 10-14 consecutive days.
 - (ii) If response, taper by 20% every 5 days until off.
 - (iii) If GVHD worsens during taper, steroids should be increased to previous dose. During steroid taper, maintain therapeutic tacrolimus levels.
 - (iv) Patients who fail to respond to corticosteroids will be considered for standard second-line immunosuppressive therapy, e.g., mycophenolate mofetil, antithymocyte globulin photopheresis.

5.4 Restricted Medications and Measures

5.4.1 Antihypertensives

For the first five subjects enrolled, antihypertensives other than telmisartan should be discontinued at least 24 hours prior to the initiation of telmisartan. For subsequent patients initiating telmisartan at the 160 mg dose, anti-hypertensives other than study drug telmisartan should be discontinued 48 hours prior to initiation of study drug. However, subjects (including initial enrollees receiving dose escalation of telmisartan) who are already being treated for hypertension with three or more anti-hypertensive agents, will have a cardiology consult to determine if one or more of these agents should be continued during the period of telmisartan study drug treatment. When medically indicated, patients will be permitted to continue their non-telmisartan medications (other than potassium sparing agents such as ACE inhibitors, ARBs, spironolactone, or direct renin inhibitors) without the 24 or 48 hr. washout period prior to starting telmisartan.

Furthermore, patients who remain hypertensive after 4 doses of 160 mg telmisartan (4 days) as monotherapy will have appropriate additional antihypertensive medications (such as hydrochlorothiazide or amlodipine) introduced for the period of the study. These non-telmisartan drugs will be adjusted, as needed, to maintain appropriate BP. If telmisartan and hydrochlorothiazide or amlodipine are insufficient to control hypertension during the study, additional compatible antihypertensive medications may be added. Aliskiren is associated with increased risks of hypotension, hyperkalemia, and changes in renal function (including acute renal failure) compared to monotherapy. Patients cannot be on Aliskiren while on the study.

5.4.2 Agents That Increase the Risk of Renal Failure

Hyperkalemia may occur in patients on telmisartan, particularly in patients with advanced renal impairment, heart failure, on renal replacement therapy, or on potassium supplements, potassium-sparing diuretics, potassium-containing salt substitutes or other drugs that increase potassium levels. Potassium-sparing diuretics such as spironolactone, and angiotensin-

converting-enzyme (ACE) inhibitors will be discontinued prior to start of study and will not be used in conjunction with telmisartan during the study unless deemed necessary by the HCT clinical physicians, due to potential interactions leading to renal toxicity. Potassium supplements will also be discontinued, and re-started gradually if need is indicated by electrolyte monitoring. Foods high in potassium will be limited to safe levels during the period of telmisartan administration except as specifically allowed by the physician monitoring the patient's electrolyte status.

In patients who are elderly, volume-depleted (including those on diuretic therapy), or with compromised renal function, co-administration of NSAIDs, including selective COX-2 inhibitors, with telmisartan, may result in deterioration of renal function, including possible acute renal failure. These effects are usually reversible. Caution will be taken when administering NSAIDs to study subjects, and renal functions will be monitored.

